Seroprevalence of *Bordetella pertussis* antibodies and anti-pertussis antibody response after a single dose of Tdap in pregnant Thai women

NCT number: NCT 03498300

Document date: March 11, 2020

Background: Maternal immunization with tetanus toxoid, reduced diphtheria toxoid, and acellular pertussis vaccine (Tdap) has recently been implemented to prevent infant pertussis. Tdap is still not routinely recommended in Thailand, and there are limited data to support or challenge this strategy.

Objectives: The primary aim was to determine the seroprevalence of anti-pertussis toxin antibodies (anti-PT IgG) among pregnant Thai women. The secondary aims were to evaluate antibodies response after Tdap vaccination between seronegative and seropositive mothers and to compare the different antibody titers at delivery among seropositive mothers who received Tdap to those who received tetanus-diphtheria vaccine (Td).

Methods: This randomized clinical trial was conducted during April 2018 to April 2019 at Siriraj Hospital, Bangkok, Thailand. A total of 129 pregnant women were included. Paired blood samples for anti-PT IgG levels were obtained during the first antenatal visit and at delivery. A baseline cut-off value of <5 IU/ml indicated seronegativity. All seronegative participants (n=69) received Tdap, while the seropositive group were randomized 1:1 to receive either Tdap (n=18) or Td (n=13) during 27-36 weeks' gestation. The antibody levels from both sera were compared between groups.

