Statistical analysis: All data analyses were performed using PASW Statistics version 18.0 for Windows (SPSS, Inc., Chicago, IL, USA). Descriptive data are presented as number and percentage, mean \pm standard deviation, or median and range (minimum–maximum), as appropriate. One-way analysis of variance (ANOVA) and Kruskal-Wallis test was used to compare continuous variables with and without normal distribution among 3 groups, respectively. Either Pearson's chi-square test or Fisher's exact test was used to compare qualitative characteristics among groups. Comparison of anti-PT IgG levels between the first antenatal care (ANC) and during delivery in each group was performed using Wilcoxon test. Mann-Whitney U test was used to evaluate antibody response after Tdap vaccination between seronegative and seropositive mothers (group 1 vs. group 2), and to compare the different anti-PT IgG levels of paired serum samples among seropositive mothers between those who received Tdap and those who received Td (group 2 vs. group 3). Spearman's rho analyses were performed to examine the correlation of the increment of anti-PT IgG titers with the interval of Tdap vaccination and delivery. A p-value <0.05 was considered statistically significant.

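### The one vaccination-timing analysis correlates an antibody increment of unstated scale with the Tdap-to-delivery interval, without adjusting for the baseline titre that was measured

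*Combined protocol and SAP*

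**What the plan says.** The Statistical analysis section has one sentence on timing: Spearman's rho analyses, in the plural, to "examine the correlation of the increment of anti-PT IgG titers with the interval of Tdap vaccination and delivery". The outcome is described only as "the increment of anti-PT IgG titers". No covariate, stratum or analysis set is named, and none of the other methods in the section (ANOVA, Kruskal-Wallis, chi-square, Fisher, Wilcoxon, Mann-Whitney) takes a covariate.

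The Methods paragraph shows that a baseline value exists: "Paired blood samples for anti-PT IgG levels were obtained during the first antenatal visit and at delivery". Baseline also defines the groups: "A baseline cut-off value of <5 IU/ml indicated seronegativity". Tdap recipients come from both sides of that cut-off: "All seronegative participants (n=69) received Tdap", and the seropositive women were randomized to "Tdap (n=18) or Td (n=13) during 27-36 weeks" of gestation. That makes 69 + 18 = 87 Tdap recipients. The interval varies because vaccination could fall anywhere in that window; it is not described as randomized.

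**The concern.** An increment is built from baseline, so baseline can remain in it, and how much remains depends on the scale. Spearman's rho is the same for a fold rise and its logarithm, but not for a difference and a ratio. Whichever scale was used, it removes baseline cleanly only under one particular relation between baseline and delivery titre.

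If baseline remains, two things can follow. It adds scatter unrelated to timing, which costs power. If women with higher baselines also tended to have longer or shorter intervals, it can produce a correlation with no timing effect behind it. In either case the one timing result is hard to interpret, when the measurement needed to adjust it was already in hand.

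**Working it through.** The plan gives no sample size, power or correlation for this analysis, so there is no figure to reproduce.

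**Inputs from the documents.** n = 87 (pooled), 69 (seronegative) or 18 (seropositive); cut-off 5 IU/ml; vaccination at 27–36 weeks; significance at 0.05 (two-sided assumed).

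**Assumed inputs.** Median baseline 3 IU/ml. SD of log10 baseline σ_B = 0.29–0.47 pooled and 0.22–0.34 in the seronegative group. Residual SD σ_e = 0.3 or 0.4 log10. For power, a timing slope of 0.03 log10 per week and delivery at 37–40 weeks.

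**Model.** With B = log10 baseline, D = log10 delivery titre and T = interval: D = a + gB + sT + e.

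- Log fold rise: D − B = a + (g − 1)B + sT + e. Baseline vanishes only at g = 1.
- Difference: when delivery titres are well above baseline, its ranks nearly follow D, which contains gB. Baseline nearly vanishes only at g = 0.

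So a fold rise is mismatched at g = 0 and a difference at g = 1.

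**Spread of the interval.** If vaccination is uniform over 27–36 weeks and delivery independently uniform over 37–40, the variance of T is 9²/12 + 3²/12 = 6.75 + 0.75 = 7.5, SD 2.74 weeks. (Taking T as uniform over 1–13 weeks would give 12/√12 = 3.46, which does not follow from those premises and inflates power.)

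**Power with a mismatched scale (fold rise, g = 0, n = 87).** Timing signal: 0.03 × 2.74 = 0.082. Unadjusted correlation: r = 0.082/√(0.082² + σ_B² + σ_e²), converted to Spearman by (6/π)·asin(r/2), with z = atanh(rho)·√((n − 3)/1.06). Adjusted regression: r = 0.082/√(0.082² + σ_e²), with z = atanh(r)·√(n − 4). Power ≈ Φ(z − 1.96).

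| σ_B, σ_e | Spearman r → rho → z → power | Adjusted r → z → power | Loss |
|---|---|---|---|
| 0.47, 0.3 | 0.146 → 0.139 → 1.25 → 24% | 0.264 → 2.46 → 69% | 45 points |
| 0.29, 0.4 | 0.164 → 0.157 → 1.41 → 29% | 0.201 → 1.86 → 46% | 17 points |

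Simulation with this interval distribution gives about 15–45 points across both mismatches. An independent simulation (natural-log baseline SD 1, residual SD 0.8, slope 0.25 per SD of interval, n = 87) shows both the harm and its absence. Power at g = 0.2, 0.6 and 1.0 was 76%, 64%, 47% for the difference and 50%, 68%, 78% for the fold rise, against 73–77% with rank-based adjustment.

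**False association (s = 0, correlation ρ = 0.3 between baseline and interval, fold rise, g = 0).** |r| = 0.3σ_B/√(σ_B² + σ_e²). The spread of T drops out.

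| n | σ_B, σ_e | \|r\| → rho → z | False rejection |
|---|---|---|---|
| 87 | 0.47, 0.3 | 0.253 → 0.242 → 2.20 | Φ(0.24) = 59% |
| 87 | 0.29, 0.4 | 0.176 → 0.168 → 1.51 | Φ(−0.45) = 33% |
| 69 | 0.34, 0.3 | 0.225 → 0.215 → 1.73 | Φ(−0.23) = 41% |
| 69 | 0.22, 0.4 | 0.145 → 0.138 → 1.10 | Φ(−0.86) = 20% |

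Simulation over both mismatches gives 30–62% at n = 87 and 16–40% at n = 69, against 4–6% for the adjusted regression. With the matching scale, Spearman rejects in about 4–10%. With ρ = 0 every method stays at about 4–6%.

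**Sign.** In the independent simulation at g = 0.6, ρ = 0.3 and no timing effect, the mean rho was +0.14 for the difference and −0.12 for the fold rise: opposite signs from one model.

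**Precision.** At rho = 0 the 95% half-width, tanh(1.96·√(1.06/(n − 3))), is 0.22 at n = 87, 0.24 at n = 69 and 0.48 at n = 18.

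**The case against.** The strongest reply is that nothing is shown to be wrong. Spearman is a sensible choice for skewed titres, it is valid when baseline and interval are unrelated, and with a matching scale it loses almost nothing. Harm needs a mismatch, and a false association needs a baseline–interval relation as well; the documents show neither. All of this stands, and it limits the point.

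It can also be said that an increment ordinarily means an amount added. On that reading the fold-rise figures do not apply, and the difference suffers most only as delivery titre approaches proportionality to baseline. That is a fair reading, but the text does not settle it. Likewise, the plural in the Spearman sentence may mean separate runs by group. That would narrow the baseline range and reduce the bias without removing it, as the n = 69 figures show, and the text does not say it was done.

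Timing is not among the stated aims, and no conclusion of no timing effect is drawn. Both are correct.

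A reader might go further and infer that the trial's timing correlation is an artefact, or that a real effect was missed. The documents give no rho, no baseline–interval relation and no baseline–delivery relation, so they support neither inference. Nor should the point become a call for a curvature term: Spearman and a linear regression can both miss a mid-range peak, but that is separate from baseline adjustment and would be another post hoc choice.

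**Conclusion.** The point holds as a minor, exploratory improvement. Three things are plain from the text: this is the only timing analysis, the scale of the increment is not stated, and baseline is not adjusted for although it was measured. The consequence is conditional. With a matching scale and no baseline–interval relation there is essentially none. With a mismatch, the power loss is roughly 15–45 points at n = 87. With a mismatch and a baseline–interval correlation of 0.3, false rejection is roughly 30–60% at n = 87 and 16–40% at n = 69, against about 5% after adjustment.

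These sizes rest on assumed baseline and residual spread and, for power, an assumed slope and delivery window. They show what is possible, not what happened in this trial. The primary and secondary aims are unaffected. The unstated scale and analysis set are missing detail; the lack of baseline adjustment is the substantive part.

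**What to change.** Keep the Spearman result as descriptive, saying whether the increment is a difference or a ratio and which women are included. Add one exploratory analysis among Tdap recipients that adjusts for baseline, in one of two forms:

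- a partial Spearman correlation of delivery titre with the interval, given baseline titre, which is robust to skewed or heavy-tailed titres; or
- a regression of log10 delivery titre on the interval and log10 baseline, with a stated rule for any baselines below the assay limit.

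Report the estimate with a 95% CI, and do not read a null result as showing no timing effect.

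The cost is one analysis of data already collected. It must be labelled post hoc: "This randomized clinical trial was conducted during April 2018 to April 2019", and the document is dated March 2020. The rank version gives up some power when residuals are normal, and the regression does so when they are heavy-tailed. Coarse handling of low baselines leaves adjustment incomplete: if values below 2 IU/ml were set to 1 IU/ml (both assumed), false rejection in simulation was 4–9% at a baseline–interval correlation of 0.2–0.3.
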